11.2 Purpose

Adverse event data collection and reporting, which are required as part of every clinical trial, are done to ensure the safety of patients enrolled in the studies as well as those who will enroll in future studies using similar agents. Adverse events are reported in a routine manner at scheduled times during a trial (please follow directions for routine reporting provided in the Data Reporting Section). Additionally, certain adverse events must be reported in an expedited manner for more timely monitoring of patient safety and care. The following sections provide information about expedited reporting.

Events resulting from concurrent illnesses and reactions to concurrent medications must be reported as adverse events.

Any worsening of the patient's clinical condition while the patient is on study will be considered to be an adverse event unless it is within the normal range of disease fluctuation for that patient.

11.2.1 Determination of Reporting Requirements

Reporting requirements may include the following considerations:

- 1) whether the patient has received an investigational or commercial agent;

2) the characteristics of the adverse event including the grade (severity), the relationship to the study therapy (attribution), and the prior experience (expectedness) of the adverse event;

3) the Phase (1, 2, or 3) of the trial; and 4) whether or not hospitalization or prolongation of hospitalization was associated with the event.

11.2.2 Steps to determine if an adverse event is to be reported in an expedited manner:

Step 1: Identify the type of event using the NCI Common Toxicity Criteria (CTC).

The CTC provides descriptive terminology and a grading scale for each adverse event listed. A copy of the CTC can be downloaded from the CTEP home page (<http://ctep.cancer.gov>). Additionally, if assistance is needed, the NCI has an Index to the CTC that provides help for classifying and locating terms. All appropriate treatment locations should have access to a copy of the CTC.

Step 2: Grade the event using the NCI CTC.

Step 3: Determine whether the adverse event is related to the protocol therapy (investigational or commercial).

Attribution categories are as follows: Unrelated, Unlikely, Possible, Probable, and Definite.

Step 4: Determine the prior experience of the adverse event.

11.3 Reporting Methods – n/a

11.3.5 FDA Reporting

N/A

11.3.6 IRB Reporting

11.3.6.1 All adverse events that are serious adverse events **and** are unexpected **and** are related or possibly related IRB within ten (10) working days of being made known to the Principal Investigator. Events that are more frequent than anticipate or more severe than expected must be reported to the IRB within ten (10) working days of being made known to the Principal Investigator.

All unanticipated deaths must be reported to the IRB within 24 hours of being made known to the Principal Investigator.

11.3.7 Follow-up Reporting

For all SAE's, the investigator is obligated to pursue and provide follow-up reporting information until the event has resolved or until an acceptable medical endpoint has been reached or the patient is lost to follow-up.

12.0 CRITERIA FOR DISCONTINUATION OF THERAPY

Treatment will be stopped for grade 4 acute toxicity (according to the current version of Common Terminology Criteria for Adverse Events (CTCAE version 4), but may be resumed per protocol if the treatment break is less than 10 working days. If grade 4 toxicity resolves beyond the 10 days the treating physician will decide whether to give additional RT.

Treatment will be stopped if metastasis is detected by radiographic or pathologic evidence and the patient will be removed from the study. A work-up for metastasis during treatment will only be carried out if the treating physician deems necessary.

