4.15 Duration of Therapy

- Within 4 weeks of enrollment, patients will be biopsied (patient may refuse) and fiducial markers placed.
- LHRH agonist androgen deprivation therapy: LHRH agonist therapy may start up to two months prior to signing consent form or any time after signing consent form, up to two weeks after fiducial marker placement (preferred) in men with intermediate or high (optional) risk prostate cancer. All patients may receive 4-6 months (+/- 2 months) LHRH agonist therapy.
- Anti-androgen treatment should begin 1-14 days prior to LHRH agonist injections. Anti-androgen will be continued four 4 months.
- .
- Standard fraction RT: Day 2 of radiotherapy will start within 32 hr of LEAD RT and will consist of 38 fractions at 2.0 Gy over 7.5 weeks
- Treatment will be stopped for grade 4 acute toxicity (according to the current version of Common Terminology Criteria for Adverse Events (CTCAE version 4), but may be resumed per protocol if the treatment break is less than 10 working days. Since we have never observed grade 4 toxicity acutely using IMRT (conformal CyberKnife treatment is an IMRT-like treatment),

such an event is unlikely. If grade 4 toxicity resolves beyond the 10 days the treating physician will decide whether to give additional RT.

- Treatment will be stopped if metastasis is detected by radiographic or pathologic evidence and the patient will be removed from the study, but not from intent-to-treat analysis. A work-up for metastasis during treatment will only be carried out if the treating physician deems necessary.
- Multiparametric MRI exams of the prostate/pelvis will be carried out after RT at 3 months, 9 months, and within 2 months of the post-treatment prostate biopsies.
- Prostate biopsies will be taken at 2-2.5 years post completion of all therapy.

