6.0 DOSING DELAYS/DOSE MODIFICATIONS

6.1 Study Agent

The study agent in this protocol is radiation, to be delivered in an innovative and investigational manner. The experimental component of the treatment is a single high-dose fraction of LEAD radiation, a dose of 12-14 Gy to be delivered to the multiparameter MRI identified tumor lesion(s). As described above, a standard radiation dose used for treatment of prostate cancer is 76 Gy at 2.0 Gy per day. This will be begun the day after the LEAD RT treatment (total dose for all treatments of 88-90 Gy and 149 Gy_{3.0} in 2.0 Gy equivalents).

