- *Failure-free Survival (FFS)*: The elapsed time from study enrollment to first documented evidence of biochemical or clinical failure or death from any cause, whichever occurs first. In the absence of any event defining failure, follow-up time will be censored at the date of last documented failure-free status.
- *Overall Survival (OS)*: The elapsed time from study enrollment to death from any cause. For surviving patients, follow-up will be censored at the date of last contact.
- *Biomarker expression*: Quantification of the amount of the biomarker specific immunohistochemical staining in the area of tumor
- *QOL*: Two contemporary instruments will be utilized to assess patient function and bother (Expanded Prostate Cancer Index Composite-SF12 (EPIC-SF12)), and prostate cancer-specific anxiety (Memorial Anxiety Scale for Prostate Cancer patients (MAX-PC)).

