14.4 Interim Monitoring

We propose the following guidelines for the Sylvester Data and Safety monitoring Committee (DSMC) (see also Appendix III) in its review of accumulating data on toxicity and feasibility of study treatment. The proposed guidelines were developed using Bayesian methods, which can be applied at any stage of enrollment without advance specification of the number of interim analyses to be performed, or the number of patients evaluable for toxicity, or response, at the time such assessments are made.^{95,96}

Under the Bayesian method, we assign a prior probability (level of belief at the start of the trial) to a range of possible values for the true toxicity rate, and likewise for the true feasibility rate. As data on treated patients become available, each of these probability

Number of Patients With acute treatment Related Grade 3+ GI/GU Toxicity	Total Patients Evaluated	Observed Rate
2	3 to 6	≥33% (2 of 6)
3	7 of 11	≥27% (3 of 11)
4	12 to 16	≥25% (4 of 16)
7	17 to 25	≥25% (7 of 25)

distributions is revised and the resulting posterior probability becomes the basis for recommending either early termination or continuation of the study. In the sections that follow, we provide specific stopping guidelines based on posterior probabilities for monitoring toxicity and efficacy over the course of this trial. Underlying assumptions for the prior distributions are also presented.

Stopping rules for safety: The following early stopping guidelines, which are based on a Bayesian method, will be

applied to ensure safety of this Phase I trial. Safety monitoring will be based on the occurrence of treatment related (possible, probable, or definite) grade 3 or higher GI or GU toxicity occurring during study treatment or within 30 days of treatment completion. Early stopping (suspension and possibly termination) will be considered if there is evidence that the proportion of patients experiencing such toxicity exceeds 15%. Specifically, we suggest as a guideline for early termination a posterior probability of 80% or higher that the rate of grade 3 or higher GI/GU toxicity exceeds 15%. **Table 2** shows specific instances where this guideline is met, thus suggesting early termination due to evidence of excessive toxicity.

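### Metastasis found during radiotherapy takes a fully LEAD-treated patient off study, an undefined status that leaves his toxicity and survival follow-up unstated (minor, cheap to fix)

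*Combined protocol and SAP*

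**What the plan says.** Two sections carry the rule. Section 12.0 (Criteria for Discontinuation of Therapy) reads: "Treatment will be stopped if metastasis is detected by radiographic or pathologic evidence and the patient will be removed from the study". Section 4.15 (Duration of Therapy) says that "the patient will be removed from the study, but not from intent-to-treat analysis". Both add that looking for metastasis during treatment is discretionary: "A work-up for metastasis during treatment will only be carried out if the treating physician deems necessary".

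On exposure, Section 6.1 says: "The experimental component of the treatment is a single high-dose fraction of LEAD radiation". Of the standard 2 Gy course it says: "This will be begun the day after the LEAD RT treatment". Section 4.15 gives that course as 38 fractions over 7.5 weeks.

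On endpoints, the safety rule in Section 14.4 counts grade 3 or higher, treatment-related GI or GU "toxicity occurring during study treatment or within 30 days of treatment completion". For overall survival, Section 9.1 says: "For surviving patients, follow-up will be censored at the date of last contact". Section 5.3 schedules side-effect assessment at 6 weeks, 3 months and then six-monthly to 5.25 years. Section 9.1 already counts radiographic metastasis as a clinical failure.

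On who is analysed, Section 3.3.1 excludes only enrolled patients who did not receive LEAD. Section 14 defines no intent-to-treat population, and Section 14.5 (Reporting and Exclusions) is marked not applicable.

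**The concern.** The rule joins two separate acts: stopping treatment, and ending the patient's participation. The paragraph just before it in Section 12.0, on grade 4 acute toxicity, does only the first. The metastasis paragraph does both, for a man who has already received the one fraction that the trial was set up to test.

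He belongs to the exposed group for the primary objective, feasibility and toxicity. If site staff read removal in its ordinary sense, his remaining acute toxicity, all his late toxicity, his quality-of-life scores and his survival status might not be collected. His survival time would then be censored at last contact, just after a finding that worsens his prognosis. That is informative censoring, and it pushes estimated survival upward.

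A man whose metastasis is found shortly after the last fraction is treated differently. He has a clinical failure under Section 9.1, and no rule ends his visits. Two similarly exposed patients would be followed differently because of when a discretionary scan was done. Keeping the first man in an analysis, as Section 4.15 does, does not create data that nobody was told to collect.

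**Working it through.** The plan states no figure on this point, so there is none to reproduce. The check compares the sections and then shows scale.

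**1. Is the experimental dose complete when the rule applies?** Yes. LEAD is one fraction, and the 38 standard fractions start the next day (6.1). Any metastasis found during those 38 fractions is found after full LEAD exposure.

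**2. What happens to his data?**

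| Section | What it requires | Does it settle follow-up after removal? |
|---|---|---|
| 4.15 | Off study, kept in intent-to-treat analysis | No; addresses analysis only |
| 12.0 | Off study | No; silent on analysis and follow-up |
| 3.3.1 | Excludes only patients not given LEAD | Supports keeping him in the analysis |
| 11.3.7 | Follow SAEs to resolution, an acceptable endpoint or loss to follow-up | Only for SAEs; a grade 3 GI/GU event need not be serious |
| 13.0 | Data for all registered patients, as the protocol requires | No; no requirement is written for a removed patient |
| 15.5 | A CRF for anyone given any study treatment | A form, not a visit schedule |
| Appendix IV | Off-treatment, relapse and death forms | Some data; no visit schedule after removal |

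Some data are plainly expected. No section says that the scheduled visits continue, and none says that they stop.

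**3. When does his acute window close?** Section 14.4 ends it 30 days after treatment completion. Appendix IV names discontinuation and completion as separate events, so a man stopped early has no clear end date. If he is the third patient, the 30-day observation that must pass before the fourth enrolment has no clear start. The gap affects any early stop, including one for grade 4 toxicity.

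**4. Scale.** These figures assume one or two men lost. They do not estimate how often that would happen.

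- Weight of one man: 1/25 = 4% of the trial, or 1/3 of the lead-in.
- No events seen, exact 95% upper limit 1 − 0.025^(1/n): n = 25 gives 13.7%, n = 24 gives 14.2%, n = 23 gives 14.8%. Losing an event-free man costs little.
- The lost man had an event: 3/25 = 12.0% becomes 2/24 = 8.3% if he leaves the denominator, or 2/25 = 8.0% if he stays in and is counted as event-free.
- First boundary of Table 2 in Section 14.4 (2 of 6). The posterior is Beta(a + x, b + n − x), and the guideline is P(rate > 15%) ≥ 0.80. The printed prior, Beta(0.2, 1.8), has mean 0.2/2.0 = 10%, not the stated 15%. Beta(0.3, 1.7) has mean 0.3/2.0 = 15%. Both are shown.

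| Data | Beta(0.3, 1.7) | Beta(0.2, 1.8) |
|---|---|---|
| 2 of 6 (event seen) | 0.80 | 0.78 |
| 1 of 5 (man dropped) | 0.52 | 0.47 |
| 1 of 6 (kept, event not seen) | 0.45 | 0.41 |

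Table 2 as printed calls for stopping at 2 of 6. With one event unseen it would not.

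**5. Which endpoints are affected?** Acute and late toxicity, quality of life and overall survival. Failure-free interval and failure-free survival hardly move, because the metastasis is itself the event and is dated when first documented.

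**The case against.** Three stronger readings are tempting, and the documents do not support them.

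*Follow-up ends on removal.* This is an inference. The sentence sits under a heading about stopping therapy, and Sections 11.3.7, 13.0, 15.5 and Appendix IV all point towards some continued data, with no exception for removed patients. This objection stands against any statement that follow-up does end. It does not close the gap, because none of those sections gives a removed patient a visit schedule for non-serious toxicity, late effects or survival.

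*Sections 4.15 and 12.0 contradict each other on analysis.* They do not. Section 12.0 is silent where 4.15 is explicit, and 4.15 read with 3.3.1 keeps him in. Nor does the pointer to 12.0 in Section 5.4 give that section precedence; it is only a cross-reference. What remains is an omitted clause and an undefined analysis set.

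*Survival is materially biased.* One unrecorded death would move a crude proportion from 24/25 = 96% to 100%. That requires metastasis found within 7.5 weeks and a later death that goes unrecorded despite the death form. Section 14.2 expects deaths to be rare and includes the survival endpoints for completeness. The direction of the bias is clear, but its size is speculative.

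It is also fair that the lead-in is defined by the first three patients enrolled, so removal does not change who is in it, and that toxicity arising during treatment counts in any case. Only its clock is uncertain.

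**Conclusion.** The point holds as a gap in the wording with a possible effect on the primary safety data. Removal from the study is undefined for a man who has had the full LEAD dose, 12.0 omits the clause in 4.15 on analysis, Section 14 defines no intent-to-treat set, and the acute window has no clear end when radiotherapy stops early. If the wording were applied in its ordinary sense, he would be incompletely observed for toxicity and informatively censored for survival.

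The expected effect is small. Work-up during treatment is discretionary, the documents give no rate of metastasis in this period, and the expected number therefore cannot be calculated. Assuming 0 to 2 of 25, the loss is 0 to 8% of patients (2/25 = 8%). It changes little unless a lost man carries a grade 3 or higher event, in which case it could alter a stopping recommendation. Severity is minor. It is a cheap improvement, worth making beforehand because visits that were never made cannot be recovered later.

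**What to change.** Reconcile Sections 4.15 and 12.0 so that they carry the same text, covering three things:

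1. A patient whose radiotherapy is stopped for metastasis is off protocol radiotherapy but stays on study for the scheduled toxicity and survival follow-up, as far as he agrees.
2. The acute window runs to 30 days after the last fraction actually given. Use the same anchor in 9.1 and 14.4, including the lead-in, so that every early stop is covered.
3. All LEAD-treated patients stay in the toxicity, failure and survival analyses. Either define the intent-to-treat set in Section 14 or replace the term with this description.

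Nothing here changes when or whether radiotherapy is stopped, and 9.1 already supplies the failure event. The cost is a few sentences of protocol text and a few follow-up contacts for the rare patient affected.

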13.0 DATA REPORTING

Data will be submitted according to the protocol requirements for ALL patients registered. Patients for whom documentation is inadequate to determine eligibility will generally be deemed ineligible.

A list of forms to be submitted, as well as submission schedule, may be found in Appendix IV.

14.0 STATISTICAL CONSIDERATIONS

14.1 Sample Size/Accrual Rate

Twenty five (25) patients will be enrolled over a two-year period, subject to early stopping rules for safety (grade 3 or higher treatment-related acute GU/GI toxicity) and feasibility (LEAD eligibility). Study size is intended to provide initial evidence of safety and feasibility of the proposed treatment as a basis for planning Phase II efficacy trial.

14.2 Analysis Plan

Study findings will include descriptive statistics summarizing patient baseline characteristics, RT planning parameters and treatment received⁹⁴. A detailed safety profile will be provided consisting of lists and tabulations of all adverse events indicating type, grade, attribution to treatment and time of onset relative to treatment according to CTCAE standards. This will be done separately for acute and late toxicity (see Section 9.1). Patient level summaries will include worst grade toxicity and the number and duration of treatment delays attributable to toxicity.

Feasibility will be assessed by reporting the proportion of enrolled patients who are administered LEAD dose following successful MRI-guided planning and corresponding 95% confidence interval (CI) using the exact binomial method. The same method will be used to estimate the two-year positive biopsy rate defined as the proportion of positive biopsy findings among patients without clinical or biochemical failure two years after completing study treatment.

Clinical outcome will be further assessed by estimating the rate of biochemical failure, as defined in Section 9.1, using the method of cumulative incidence allowing for competing risk of death without biochemical failure. Biochemical failure free survival will be estimated by the Kaplan Meier method. Similar analysis will be provided for the combined rate of biochemical and clinical failure (cumulative incidence) and failure free survival (Kaplan Meier). Although death of study patients during the planned follow up period is expected to be rare and not attributable to prostate cancer, we include these survival endpoints (biochemical failure-free, failure-free, and overall survival) for completeness.

We will summarize the scores of QOL assessments with descriptive statistics and apply mixed effects modeling to evaluate changes over time.

Finally, to the extent permitted by available data from baseline biopsies, exploratory analysis will be performed to investigate the relationship between the level of biomarker expression in tumor tissue within vs. outside the DCE-MRI determined region and the correlation between these measures and Gleason score. Analysis of the sequential imaging studies will correlate the presence/absence of DCE enhancing area and its volume with biopsy positivity at 2 – 2.5 years. We will attempt to establish the ability of MRI for early assessment of RT outcome.

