2.0 OBJECTIVES

2.1 Primary Objective

- To determine the feasibility and toxicity of LEAD RT in a Phase I clinical trial.

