9.1 Definitions

- *Feasibility*: The proportion of enrolled patients for whom LEAD RT dose can be successfully administered following MRI-guided planning.
- *Acute toxicity*: Grade 2 or higher treatment-related acute GU/GI toxicity occurring during treatment and within 30 days of completing treatment. The severity of the reactions to the treatment is scored according to the criteria outlined in Appendix II.
- *Late toxicity*: Delayed toxicities are usually related to urinary, rectal, and sexual function. The anticipated urinary and rectal toxicities and severity criteria are shown in Appendix II.
- *Biopsy failure rate*: The proportion of positive biopsy findings among patients without clinical or biochemical failure 2-2.5 years after completing study treatment.
- *Biochemical failure-free interval (BFFI)*: The elapsed time from study enrollment to first documented evidence of biochemical failure ($PSA \geq \text{nadir}+2$). In the absence of biochemical failure, follow-up time will be censored at the date of last documented biochemical failure-free status.
- *Biochemical failure (BF) rate*: The cumulative incidence of BF allowing for competing risk as needed.
- *Biochemical failure-free survival (BFFS)*: The elapsed time from study enrollment to first documented evidence of biochemical failure or death from any cause, whichever occurs first. In the absence of any event defining biochemical failure, follow-up time will be censored at the date of last documented biochemical failure-free status.
- *Failure-free interval (FFI)*: The elapsed time from study enrollment to first documented evidence of biochemical or clinical failure. Clinical failure is defined as local failure due to newly identified extension outside of the prostate after initial regression, or urinary obstructive symptoms with carcinoma found at TURP or regional/distant failure due to radiographic evidence metastasis (nodal or hematogenous spread). In the absence of any event defining failure, follow-up time will be censored at the date of last documented failure-free status.
- *Failure rate*: The cumulative incidence of biochemical or clinical failure allowing for competing risk as needed.

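### Toxicity is half of the primary objective, but 14.2 gives it no stated proportion, denominator or interval, and late toxicity is only tabulated

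*Combined protocol and SAP*

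**What the plan says.** The primary objective in 2.1 is "To determine the feasibility and toxicity of LEAD RT in a Phase I clinical trial". Section 14.1 sets the size without a precision or power calculation ("Twenty five (25) patients will be enrolled over a two-year period, subject to early stopping rules for safety") and gives its purpose: "Study size is intended to provide initial evidence of safety and feasibility of the proposed treatment as a basis for planning Phase II efficacy trial".

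Section 14.2 then treats the endpoints differently:

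- **Toxicity (primary):** "lists and tabulations of all adverse events indicating type, grade, attribution to treatment and time of onset", done separately for acute and late events, and then "Patient level summaries will include worst grade toxicity and the number and duration of treatment delays attributable to toxicity".
- **Feasibility (primary):** a proportion with the "corresponding 95% confidence interval (CI) using the exact binomial method".
- **Positive biopsy rate (secondary):** the same exact method.
- **Biochemical failure (secondary):** cumulative incidence, with death without biochemical failure as a competing risk.

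Two grade thresholds appear. Section 9.1 defines the acute toxicity endpoint as "Grade 2 or higher treatment-related acute GU/GI toxicity" up to 30 days after treatment. Section 14.1 ties the safety stopping rule to "grade 3 or higher treatment-related acute GU/GI toxicity". Section 14.4 uses that grade 3+ event over the same window, with a guideline to consider stopping when the posterior probability of a rate above 15% reaches 80%. For late toxicity, 9.1 gives neither a grade threshold nor a time point. Follow-up visits with toxicity assessment run to 5.25 years (5.3, Appendix I).

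**The concern.** One half of the primary objective has less specified analysis than two secondary endpoints. The grade cut, the denominator and the measure of uncertainty for the main toxicity result are left open, so they could be settled after the data are seen.

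Two consequences follow. First, the only numerical toxicity rule in the plan is the monitoring guideline in 14.4. If the trial completes without meeting it, nothing in 14.2 obliges the report to show how high a rate the data still allow, and these results are meant to support planning of a Phase II trial. Second, late events accrue over more than five years. A count over all treated patients treats a man lost at one year as if he had been observed event-free to the end.

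**Working it through.** **1. What the plan's own figures give.** N = 25 is stated without inputs and cannot be re-derived. The only toxicity calculation is the Beta posterior in 14.4. Its printed parameters, Beta(0.2, 1.8), have mean 0.2/(0.2 + 1.8) = 10% and P(rate > 15%) = 21.6%, against the stated 15% and 32%. Beta(0.3, 1.7) has mean 0.3/2 = 15% and P(rate > 15%) = 32.3%, which match. It also reproduces the first three rows of Table 2: 2/6 gives 80.1%, 3/11 gives 80.1% and 4/16 gives 80.9%. That discrepancy is a separate matter. Both priors are carried below so that nothing here depends on it.

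**2. The interval that 14.2 already uses for feasibility, applied to toxicity.** For x patients with an event among n, the exact (Clopper-Pearson) 95% limits are:

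- lower = 2.5% quantile of Beta(x, n − x + 1), or 0 if x = 0
- upper = 97.5% quantile of Beta(x + 1, n − x)

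For x = 0 and n = 25 the upper limit is 1 − 0.025^(1/25) = 1 − 0.8628 = 13.7%.

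| Patients with event / treated | Proportion | Exact 95% CI |
|---|---|---|
| 0/25 | 0% | 0 to 13.7% |
| 1/25 | 4% | 0.1 to 20.4% |
| 2/25 | 8% | 1.0 to 26.0% |
| 3/25 | 12% | 2.5 to 31.2% |
| 5/25 | 20% | 6.8 to 40.7% |

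Only zero events puts the upper limit below 15%. If 20 patients were treated, 0/20 would give 0 to 16.8%.

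**3. What an uncrossed boundary can conceal.** Take 5 events in 25 patients. The final posterior is Beta(0.2 + 5, 1.8 + 20) = Beta(5.2, 21.8) under the printed prior, or Beta(5.3, 21.7) under the alternative. P(rate > 15%) is then 68.8% or 70.6%. This is below the 80% criterion and below the printed last row of Table 2 (7 events for 17 to 25 patients).

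The route to 5/25 matters, because earlier rows could have been met on the way. A route that meets none exists: at most 1 event through patient 6, 2 through patient 11 and 3 through patient 16, with the fifth event at patient 22 or later. It also stays below the 80% criterion at every stage under both priors, since 5 events reach 80% only up to n = 21. The trial could therefore finish uncrossed with a rate more likely above 15% than below it.

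**4. Late toxicity.** With incomplete follow-up, the crude proportion counts unobserved time as event-free, so it is biased downwards if those lost have a risk similar to those who stay. The documents give no drop-out figure, so the size is unknown. As an assumption only, suppose 3 late events, with 0, 5 or 10 of the 25 lost very early without an event. The crude figure is 3/25 = 12% in all three cases. Among those actually followed it is 3/25 = 12%, 3/20 = 15% or 3/15 = 20%.

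**The case against.** The strongest reply has four parts.

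- **The rate can be derived.** The worst-grade summary in 14.2 yields the grade 2+ and grade 3+ counts for at most 25 men. That is correct. A reader might infer that the plan produces no patient-level toxicity data, and it does not support that. What is missing is the stated proportion, denominator and interval.
- **The two grades do not conflict.** A reader might infer that 9.1 and 14.1/14.4 define the endpoint in contradictory ways. They do not: 9.1 defines an endpoint and 14.1/14.4 define a monitoring trigger, and a stricter trigger is ordinary. 14.2 also refers to 9.1. This stands, and it argues for reporting both grades, not for replacing one by the other.
- **15% is only a monitoring threshold.** The plan never claims to exclude 15% at the end, and 14.1 promises no more than initial evidence. This also stands. The intervals show what 25 patients can say; they do not show that the trial fails a test it set itself. Nor do the documents say that an uncrossed boundary will be reported as proof of safety.
- **The late-toxicity gain may be small.** 14.2 expects deaths to be rare and records time of onset. The competing-risk element may indeed change little. The benefit comes mainly from handling incomplete follow-up.

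That Phase I safety is descriptive does not dispose of the point. An exact interval is descriptive, and the plan already uses one for feasibility at the same sample size.

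**Conclusion.** The point holds as a gap in specification. Toxicity is co-primary, yet 14.2 names no proportion, denominator or interval for it, while extending exact intervals to feasibility and the biopsy rate and competing-risk estimation to biochemical failure. With 25 treated patients the unreported uncertainty is large: the upper 95% limit is 13.7% with no events, 20.4% with one and 40.7% with five. The report should therefore not present an uncrossed stopping boundary as evidence that the rate is below 15%.

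The interval figures assume that all 25 patients receive LEAD and are evaluable to 30 days; with fewer, they widen. The posterior figures hold under either prior to within about two percentage points. The direction of bias in crude late counts depends on incomplete follow-up being unrelated to risk, and its size cannot be obtained from the documents.

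This is worth changing before analysis, because it fixes how half of the primary objective is answered. It does not show that the design is unsafe or that its sections contradict each other on grade.

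**What to change.** Add to 14.2:

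1. The proportion of LEAD-treated patients with treatment-related acute GI/GU toxicity to 30 days after treatment, at grade 2+ (the 9.1 definition) and at grade 3+ (the monitored event), each with an exact 95% CI. The LEAD-treated denominator fits 3.3.1, which drops patients not given LEAD.
2. The final posterior probability that the grade 3+ rate exceeds 15%, as a descriptive figure, computed once the prior parameters in 14.4 have been reconciled with their stated mean and tail.
3. Cumulative incidence of late grade 2+ and grade 3+ GI/GU toxicity, with death as a competing risk, patients censored at last toxicity assessment, and the time origin and reporting times stated.
4. A sentence that an uncrossed Table 2 boundary will not be reported as showing a rate below 15%.

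The cost is a few lines of text and a little more analysis with methods already in the plan. The sample size, visits and monitoring guideline are untouched. The drawback is a safety statement that looks less favourable, because the width of the intervals becomes visible.
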